10.15. Appendix 15: Management of Infusion Related Reactions

NCI CTCAE Severity G1-ade	Treatment Modification
Grade 1 - mild Mild transient reaction; infusion interruption not indicated; intervention not indicated.	Decrease the infusion rate by 50% and monitor closely for any worsening.
Grade 2 - moderate Therapy or infusion interruption indicated but responds promptly to symptomatic treatment (for example, antihistamines, NSAIDs, narcotics, IV fluids; prophylactic medications indicated for 24 hours).	Temporarily discontinue infusion. Resume infusion at 50% of previous rate once infusion-related reaction has resolved or decreased to at least Grade 1 in severity, and monitor closely for any worsening.
Grade 3 or Grade 4 - severe01·life-threatening Grade 3: Prolonged (for example, not rapidly responsive to symptomatic medication and/or brief interruption of infusion); recurrence of symptoms following initial improvement; hospitalization indicated for clinical sequelae. Grade 4: Life-threatening consequences; urgent intervention indicated.	Stop the infusion immediately and disconnect infusion tubing from the patient. Treatment should be permanently discontinued.

If infusion rate has been decreased by 50% due to an infusion reaction, it must remain decreased for the next scheduled infusion. If no infusion reaction is observed at the next scheduled infusion, the infusion rate may be returned to baseline at subsequent infusions.

10.16. Appendix 16: Abbreviations

The following is a list of abbreviations that may be used in the protocol.

Abbreviation	Term
ACTH	adrenocorticotropic hormone
ADA	Anti-drug antibodies
ADL	activities of daily living
AE	adverse event
AESI	adverse events of special interest
AIDS	acquired immunodeficiency syndrome
ALK	anaplastic lymphoma kinase
ALT	alanine aminotransferase
am	anti-mouse
ANC	absolute neutrophil count
aPTT	activated partial prothrombin time
ART	antiretroviral therapy
ASCO	American Society of Clinical Oncology
AST	aspartate aminotransferase
ASTCT	American Society for Transplantation and Cellular Therapy
AUC	area under the concentration-time curve
AUC _{inf}	area under the concentration-time versus time curve from time 0 to infinity
AUC _{last}	area under the concentration-time curve from time 0 to time of last measurable concentration
AUC _{tau,ss}	area under the steady state dose concentration-time curve over dosing interval tau
AV	atrioventricular
BLRM	Bayesian Logistic Regression Model
BNP	Brain natriuretic peptide
BOR	best overall response
BP	blood pressure
Bpm	beats per minute
BUN	blood urea nitrogen
C1D1	Cycle 1 Day 1
C1D15	Cycle 1 Day 15
C2D15	Cycle 2 Day 15
C3D1	Cycle 3 Day 1
CD4+	Cluster of differentiation 8 positive
CD8+	Cluster of differentiation 4 positive
CEA	cergotuzumab amunaleukin
CEA-IL2v	CEA-targeted IL-2 variant
cfDNA	cell free DNA
CFR	Code of Federal Regulations
CHF	congestive heart failure

Abbreviation	Term
CI	confidence interval
CIOMS	Council for International Organizations of Medical Sciences
CK	creatinine kinase
CK-MB	creatine kinase-muscle type, myocardial band
CL	total clearance of drug from eg, plasma
C _{max}	maximum observed concentration
CONSORT	Consolidated Standards of Reporting Trials
CR	complete response
CRC	colorectal cancer
CrCl	creatinine clearance
CRF	case report form
CRO	contract research organization
CRP	C-reactive protein
CRS	cytokine release syndrome
CSR	clinical study report
CT	computed tomography/clinical trial
CTC	circulating tumor cells
CTCAE	Common Terminology Criteria for Adverse Events
DCR	disease control rate
DCT	data collection tool
DILI	drug-induced liver injury
DLRM	Dose Level Review Meeting
DLT	dose-limiting toxicity
DMC	Data Monitoring Committee
DNA	deoxyribonucleic acid
DOR	duration of response
DU	dispensable unit
EC	ethics committee
ECG	electrocardiogram
ECHO	echocardiogram
ECOG	Eastern Cooperative Oncology Group
eCRF	electronic case report form
EC	exclusion criteria
EDP	exposure during pregnancy
EGFR	epidermal growth factor receptor
EMA	European Medicines Agency
EOI	end of infusion
EOS	end of study
EOT	end of treatment
EU	European Union
EWOC	escalation with overdose control
FAP	fibroblast activation protein
FAP-IL2v	FAP-targeted IL-2 variant

Abbreviation	Term
FDA	Food and Drug Administration (United States)
FFPE	formalin-fixed paraffin-embedded
FIH	first in human
FSH	follicle-stimulating hormone
GCP	Good Clinical Practice
GGT	gamma-glutamyl transferase
GH	Growth hormone
GI	gastrointestinal
GM-CSF	granulocyte-macrophage colony-stimulating factor
HCV	hepatitis C virus
HER2	human epidermal growth factor receptor 2
HIPAA	Health Insurance Portability and Accountability Act
HIV	human immunodeficiency virus
HNSTD	highest non-severely toxic dose
hPBMC	human peripheral blood mononuclear cells
hr	hour
HR	heart rate
HRT	hormone replacement therapy
IB	Investigator's Brochure
IC	inclusion criteria
ICD	informed consent document
ICH	International Council for Harmonisation
ICIs	immune checkpoint inhibitors
ICU	intensive care unit
ID	identification
IF	immunofluorescence
IFN- γ	interferon gamma
IGF-1	insulin-like growth factor 1
IHC	immunohistochemistry
IL	interleukin
IMP	investigational medicinal product
IND	Investigational New Drug
INR	international normalized ratio
IP-10	IFN- γ -inducible protein 10
IP manual	investigational product manual
IPAL	Investigational Product Accountability Log
irAE	immune-related adverse event
IRB	Institutional Review Board
IRR	Infusion-related reaction
IRT	Interactive Response Technology
ISR	injection site reaction
IUD	intrauterine device
IUS	intrauterine hormone-releasing system

Abbreviation	Term
IV	intravenous
IWR	interactive Web-based response
JAGS	just another Gibbs sampler
LBBB	left bundle branch block
LDH	lactate dehydrogenase
LFT	liver function test
LH	luteinizing hormone
LUC	large unstained cells
LVEF	left ventricular ejection fraction
mAb	monoclonal antibody
MABEL	minimum anticipated biological effect level
MAP	meta-analytic-predictive
MedDRA	Medical Dictionary for Regulatory Activities
MEK	mitogen-activated protein kinase kinase
MCMC	Markov Chain Monte Carlo Methods
ITT	Modified-intent-to-treat
MM	metastatic melanoma
MOA	mechanism of action
MRI	magnetic resonance imaging
msec	millisecond
MSS	microsatellite-stable
MTD	maximum tolerated dose
MUGA	multigated acquisition scan
N/A	not applicable
NAb	neutralizing antibodies
NCI	National Cancer Institute
NE	non-evaluable
NIMP	non-investigational medicinal product
NK	natural killer
NOAEL	no observed adverse effect level
NSAIDS	nonsteroidal anti-inflammatory drugs
NSCLC	non-small cell lung cancer
OR	overall response
ORR	objective response rate
OS	overall survival
OvCa	ovarian cancer
PBMC	peripheral blood mononuclear cell
PD	pharmacodynamics(s)/progressive disease
PD-1	programmed cell death protein 1
PD-L1	programmed death-ligand 1
PET	positron emission tomography
PFS	progression-free survival
PK	pharmacokinetic(s)

Abbreviation	Term
PR	partial response
PRL	prolactin
PS	performance status
PT	prothrombin time
PTT	partial thromboplastin time
PVC	premature ventricular contraction/complex
Q1W	once every week
Q2W	once every two weeks
Q12W	once every twelve weeks
QTc	corrected QT
QTcB	QTc corrected QT (Bazett method)using Bazett's formula
QTcF	QTc corrected QT (Fridericia method)using Fridericia's formula
qual	qualitative
R _{ac}	accumulation ratio based on AUC (observed)
RCC	renal cell carcinoma
RECIST	Response Evaluation Criteria in Solid Tumors
pSTAT5	signal transducer and activator of transcription 5 (protein)
rhIL-15	recombinant human Interleukin-15
RNA	ribonucleic acid
RO	receptor occupancy
RP2D	recommended Phase 2 dose
RR	response rate
SAE	serious adverse event
SAP	statistical analysis plan
SC	subcutaneous
SCCHN	squamous cell head and neck carcinoma
SD	stable disease
SoA	schedule of activities
SOC	standard of care
SOP	standard operating procedure
SRSD	Single-reference safety document
SUSAR	Suspected Unexpected Serious Adverse Reaction
t _½	terminal phase half-life
T4	thyroxine
TBili	total bilirubin
TGI	tumor growth inhibition
TIL	tumor infiltrating lymphocytes
TK	toxicokinetics
TNF	tumor necrosis factor
TNF-α	tumor necrosis factor-α
T _{max}	time to reach C _{max}
TME	tumor microenvironment
TSH	thyroid-stimulating hormone

Abbreviation	Term
TT	thrombin time
TTP	time to progression
UC	urothelial carcinoma
ULN	upper limit of normal
US	United States
WBC	white blood cell
WOCBP	woman of childbearing potential

1. VERSION HISTORY

This is the first version.

2. INTRODUCTION

Note: In this document any text taken directly from the protocol is *italicized*.

PF-07209960 is a fusion of a single, potency-reduced, IL-15 mutein and a bivalent high affinity anti- PD-1 full length IgG. This antibody-cytokine fusion molecule is designed to deliver PD-1-mediated avidity-driven IL-2/15 receptor stimulation preferentially to PD-1-positive CD8+ T cells, which are enriched in tumors and can mediate anti-tumor activity, while reducing the natural preference of IL-15 for majority PD-1-negative NK cells, which may mediate toxicity. The exposure of the IL-15 mutein is extended by fusing it to an antibody, which also reduces its potency to prevent systemic activation of PD-1 negative lymphocytes. Pre-clinical data suggest the stimulatory activity of PD-1 targeted IL-15 mutein is enhanced in tumor infiltrating lymphocytes preferentially over peripheral lymphocytes and can lead to anti-tumor activity greater than can be achieved with anti-PD-1 and IL-15 agonist either alone or in combination.

Study C4011001 is a FIH Phase 1 study designed to evaluate the safety, tolerability, PK, PD, and potential clinical benefits of PF-07209960 in participants with selected locally advanced or metastatic solid tumors. Presently, only monotherapy of PF-07209960 is assessed in the study, which is composed to two parts; Part 1: Dose Escalation and Part 2: Dose Expansion.

This SAP provides the detailed methodology for summary and statistical analyses of the data collected in study C4011001. This document provides additional details for the planned analyses that are outlined in the protocol. This SAP was written in reference to Amendment 1 of the protocol dated October 30, 2020 which will be the initial version of the protocol that participants will be enrolled under. The original version of the protocol dated September 15, 2020 will not be used. Any major modifications of the endpoints or analyses will be reflected in amendments to the protocol and/or SAP.

2.1. Study Objectives and Endpoints

2.1.1. Primary Objectives

2.1.1.1. Part 1

- To assess safety and tolerability at increasing dose levels of PF-07209960 in participants with select locally advanced/metastatic solid tumors in order to estimate the MTD and select the RP2D/schedule.*

2.1.1.2. Part 2

- To confirm safety and tolerability of PF-07209960 at the RP2D in participants with selected tumor types.*
- To evaluate preliminary evidence of anti-tumor activity of PF-07209960 in participants with selected tumor types.*

2.1.2. Secondary Objectives

2.1.2.1. Part 1

- *To characterize the single and multiple dose PK of PF-07209960.*
- *To evaluate the immunogenicity of PF-07209960.*
- *To evaluate preliminary anti tumor activity.*

2.1.2.2. Part 2

- *To further evaluate the PK of PF-07209960 at the RP2D.*
- *To evaluate the immunogenicity of PF-07209960.*
- *To evaluate the effect of PF-07209960 on immune cells in tumor biopsies.*
- *To evaluate preliminary anti-tumor activity through time to event endpoints.*
- *To assess overall survival of participants treated with PF-07209960.*

2.1.3. Exploratory Objectives

CCI [REDACTED]

I [REDACTED]

CCI [REDACTED]

I [REDACTED]

I CCI [REDACTED]
I [REDACTED]
I [REDACTED]
I [REDACTED]
I [REDACTED]

2.2. Study Design

This is a Phase 1, open label, multicenter, multiple dose, dose escalation, safety, PK and PD study of PF-07209960 in participants with selected locally advanced or metastatic solid tumors (anti-PD-I/PD-LI resistant NSCLC, SCCHN, RCC, UC; or anti-PD I naive OvCa and MSS CRC for whom no standard therapy is available, or would not be an appropriate option in the opinion of the participant and their treating physician, or participants who have refused standard therapy.

The study contains 2 parts, single agent dose escalation (Part 1) followed by a dose expansion at the RP2D (Part 2). The overall study design is depicted in the schema (Section 1.2 in the protocol). Successive cohorts of participants in Part 1 will receive escalating doses of PF-07209960 as SC or IV administration every 2 weeks. The first and second participant in each dose level must be enrolled >72 hours apart. BLRM guided by EWOC principle will be used to guide dose escalation process and determine the MTD/IRP2D. Part 1 will estimate the MTD/IRP2D in sequential dose escalation cohorts for PF-07209960 as single agent in participants with selected solid tumors. After the MTD/IRP2D for PF-07209960 single agent is determined, Part 2 expansion will be initiated in participants with selected solid tumors as informed by Part 1.

Number of Participants: *The total number of participants enrolled to study intervention is estimated to range from approximately 74 to 172. Approximately 14-22 participants are expected to be enrolled in Part 1 dose escalation. Each cohort in Part 2 will enroll 20-30 participants. Approximately 60-90 participants will be initially enrolled in the first three cohorts, with the option to further enroll approximately 40-60 participants in an additional two cohorts.*

Intervention Groups and Duration: *PF-07209960 will be administered as monotherapy, SC or IV infusion over 1 hour (± 10 minutes) on Days 1 and 15 in 28 day cycles as described in Section 4.3.1 in the protocol. Treatment with study intervention will continue until either disease progression, unacceptable toxicity, participant refusal, or whichever is earliest, unless the investigator and medical monitor agree to treatment beyond disease progression based on individual benefit/risk assessments or agree to discontinue treatment or the study is terminated.*

The starting dose for PF-07209960 for this FIH study has been determined to be [REDACTED] CCI [REDACTED]. The SC route has the potential to reduce the Cmax which is believed to be associated with CRS and inflammatory responses, common AEs for agents that stimulate T cells. If excessive ISR or unexpected low exposure is encountered with SC dosing, an alternative IV infusion Q2W administration may be explored. The IV dose escalation/finding would begin at a starting dose based on the available emerging clinical data (including safety/tolerability, PK, PD) from the dose escalation cohorts with SC Q2W administration. The starting dose for IV infusion is described in Section 4.3.1.2 in the protocol. All participants will be monitored during and following their first dose (regardless of SC or IV dosing) with a 72-hour inpatient hospitalization period throughout dose escalation. Participants receiving IV dosing on C1D15 will remain at the investigational site for observation for at least 8 hours following IV infusion. Participants may not be released until the investigator has confirmed the participant has not exhibited signs and symptoms of a cytokine reaction. For additional information, refer to Section 4.3.1 in the protocol. Dose modification information is provided in Section 6.6 in the protocol.

A participant is considered to have completed the study if he/she has completed all phases of the study including the end of treatment visit.

[figure not shown]
The end of the study will be the date of the last visit of the last participants or 2 years after the last participant receives their first dose (whichever occurs first). The study may also be terminated at any time at the discretion of the sponsor. Any additional treatment beyond 2 years shall be discussed and approved by the sponsor.

Biomarker Assessments: *The biomarker studies will be used to help understand the in vivo mechanism of action of the agent(s) studied as well as potential mechanisms of resistance. The studies may help in the future development of PF-07209960 as a single agent, or in combination with other compounds, and may provide information on tumor sub types that may respond to the study intervention.*

Study Schema: The study schema for dose-escalation and expansion is provided below.

[figure not shown]
Dose Escalation

Single agent BLRM dose escalation in solid tumors:
anti-PD1/PD-L1 resistant- NSCLC, SCCHN, RCC,
UC; anti-PD-I nai:Ve-OvCa and MSS CRC

[figure not shown]
Dose Expansion

Tumor specific monotherapy dose expansion
Mandatory, de novo, pre- and on-treatment
(C2DL) biopsies required in 10-15 participants

- Refer to Table I for provisional dose levels.
- Cohorts 4 and 5 to be considered for activation only after early signs of efficacy are seen in Cohorts 1, 2 and/or 3.

Table 1. Provisional Dose Levels

- The IV infusion doses are tentative IV and will be based on emerging data.
- To be determined by BLRM.

3. ENDPOINTS AND BASELINE VARIABLES: DEFINITIONS AND CONVENTIONS

3.1. Primary Endpoint(s)

3.1.1. Part 1

- *First cycle DLTs.*
- *AEs as characterized by type, frequency, severity (as graded by NCI CTCAE version 5.0; for CRS as graded by ASTCT criteria), timing, seriousness, and relationship to study therapy.*
- *Laboratory abnormalities as characterized by type, frequency, severity (as graded by NCI CTCAE version 5.0), and timing.*

3.1.2. Part 2

- *AEs as characterized by type, frequency, severity (as graded by NCI CTCAE version 5.0; for CRS as graded by ASTCT criteria), timing, seriousness, and relationship to study therapy.*
- *Laboratory abnormalities as characterized by type, frequency, severity (as graded by NCI CTCAE version 5.0), and timing.*
- *ORR as determined by RECIST version 1.1.*

3.2. Secondary Endpoint(s)

3.2.1. Part 1

- *Single dose: C_{max} , T_{max} , AUC_{tau} . If data permits, AUC_{inf} , CL/F , $t_{1/2}$.*
- *Multiple Dose: $C_{max,ss}$, $T_{max,ss}$, $AUC_{tau,ss}$. If data permits, CL_{ss}/F , $t_{1/2,ss}$, and Rac .*
- *C_{trough} at selected time points.*
- *Incidence, titers and endogenous IL-15 cross reactivity of ADA and NAb against PF-07209960.*
- *ORR, DCR as assessed using the RECIST version 1.1.*
- *Time-to-event endpoints: DOR, PFS, and TTP by RECIST version 1.1.*

3.2.2. Part 2

- *Single dose: C_{max} , T_{max} , AUC_{tau} . If data permits, AUC_{inf} , CL/F , $t_{1/2}$.*
- *Multiple Dose: $C_{max,ss}$, $T_{max,ss}$, $AUC_{tau,ss}$. If data permits, CL_{ss}/F , $t_{1/2,ss}$, and Rac .*
- *C_{trough} at selected time points.*

- *Incidence, titers and endogenous IL-15 cross reactivity of ADA and NAb against PF-07209960.*
- *Intra-tumor T cells (such as by CDS IHC) in on-treatment versus baseline tumor biopsy samples.*
- *DCR, DOR, PFS, and TTP by RECISTversion 1.1.*
- *Overall survival.*

3.3. Exploratory Endpoint(s)

[figure not shown]
CCI

[REDACTED]

I [REDACTED]

10 of 10

1 | Page

1 | 

I [REDACTED]

I [REDACTED]
I [REDACTED]
I [REDACTED]
I [REDACTED].

3.4. Baseline Variables

Baseline characteristics will be collected according to Schedule of Activities as specified in the protocol. For the primary analysis, no baseline variable will be used for stratification or as covariates in the statistical analysis for the primary endpoint. Unless otherwise specified, the baseline value is defined as the value collected at the time closest to, but prior to, starting the study intervention administration in the first cycle.

3.5. Safety Endpoints

The on-treatment period will be used for all safety assessments. The on-treatment period is defined as the period that starts with the first dose of study treatment and ends at minimum (last dose of study treatment + xx days, start of new anti-cancer therapy - 1 day). Two different on-treatment periods will be defined to capture the typical on-treatment period (where 'xx' is 28 days), as well as an extended on-treatment period (where 'xx' is 90 days) in order to identify any late onset AE/SAEs.

3.5.1. Adverse Events

Severity of adverse events will be graded according to Common Terminology Criteria for Adverse Events (CTCAE) version 5.0. Treatment-emergent AE are defined as AEs with onset date during the on-treatment period.

For the purpose of dose escalation, any of the AEs listed in section 4.3.3 of the protocol that occur during the DLT observation period (i.e., first cycle of treatment) for DLT-evaluable participants, that are attributable to the study intervention, will be classified as DLTs.

Definitions of an AE and a SAE can be found in Appendix 3 of the protocol.

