8.3.1. Time Period and Frequency for Collecting AE and SAE Information

The time period for actively eliciting and collecting AEs and SAEs (“active collection period”) for each participant begins from the time the participant provides informed consent, which is obtained before the participant’s participation in the study (ie, before undergoing any study-related procedure and/or receiving study intervention), through and including a minimum of 90 calendar days, except as indicated below, after the last administration of the study intervention.

During the long-term follow-up period in this study for survival, only SAEs will be actively elicited and collected after completion of the active collection period described above. The SAEs identified during long-term follow-up will be reported to Pfizer Safety on the CT SAE Report Form only if considered reasonably related to the study intervention.

Follow-up by the investigator continues throughout and after the active collection period and until the AE or SAE or its sequelae resolve or stabilize at a level acceptable to the investigator and Pfizer concurs with that assessment.

For participants who are screen failures, the active collection period ends when screen failure status is determined.

If the participant withdraws from the study and also withdraws consent for the collection of future information, the active collection period ends when consent is withdrawn.

If a participant definitively discontinues or temporarily discontinues study intervention because of an AE or SAE, the AE or SAE must be recorded on the CRF and the SAE reported using the CT SAE Report Form.

Investigators are not obligated to actively seek AEs or SAEs after the participant has concluded study participation. However, if the investigator learns of any SAE, including a death, at any time after a participant has completed the study, and he/she considers the event

to be reasonably related to the study intervention, the investigator must promptly report the SAE to Pfizer using the CT SAE Report Form.

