- If the investigator does not know whether or not the study intervention caused the event, then the event will be handled as "related to study intervention" for reporting purposes, as defined by the sponsor. In addition, if the investigator determines that an SAE is associated with study procedures, the investigator must record this causal relationship in the source documents and CRF, and report such an assessment in the dedicated section of the CT SAE Report Form and in accordance with the SAE reporting requirements.

Follow-up of AEs and SAEs

- The investigator is obligated to perform or arrange for the conduct of supplemental measurements and/or evaluations as medically indicated or as requested by the sponsor to elucidate the nature and/or causality of the AE or SAE as fully as possible. This may include additional laboratory tests or investigations, histopathological examinations, or consultation with other healthcare providers.
- New or updated information will be recorded in the originally completed CRF.
- The investigator will submit any updated SAE data to the sponsor within 24 hours of receipt of the information.

10.3.4. Reporting of SAEs**SAE Reporting to Pfizer Safety via an Electronic Data Collection Tool**

- The primary mechanism for reporting an SAE to Pfizer Safety will be the electronic data collection tool.
- If the electronic system is unavailable, then the site will use the paper SAE data collection tool (see next section) in order to report the event within 24 hours.
- The site will enter the SAE data into the electronic system as soon as the data become available.
- After the study is completed at a given site, the electronic data collection tool will be taken off-line to prevent the entry of new data or changes to existing data.
- If a site receives a report of a new SAE from a study participant or receives updated data on a previously reported SAE after the electronic data collection tool has been taken off-line, then the site can report this information on a paper SAE form (see next section) or to Pfizer Safety by telephone.

SAE Reporting to Pfizer Safety via CT SAE Report Form

- Facsimile transmission of the CT SAE Report Form is the preferred method to transmit this information to Pfizer Safety.
- In circumstances when the facsimile is not working, notification by telephone is acceptable with a copy of the CT SAE Report Form sent by overnight mail or courier service.

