6.1.2. Adverse Events (AEs)

- Analysis set: Safety analysis set
- Analysis methodology:

AEs will be characterized by type, frequency, severity (as graded by NCI CTCAE version 5.0, except CRS, which will be graded by ASTCT criteria (Lee et al., 2019)) timing, seriousness, and relationship to study therapy. Further description is given in Section 6.9.1. The primary focus will be on TEAEs. TEAEs is defined as any AE that occurs during the on-treatment period, defined in Section 3.5. AEs that occur after the on-treatment period may still be recorded in the clinical database and will be included in the AE listings, but will not be included in the on-treatment emergent AE summaries.

See Section 6.9.1 for details on the specific AE summaries to be provided.

- Missing data: If an AE start or stop date is missing, imputation will be performed according to Section 5.3.1. The imputed dates will be used to determine whether the AE is to be included in the TEAE summary. The missing AE start or stop dates will be listed as is in AE listings. When the CTCAE grade is missing for an AE, the AE will be excluded from the CTCAE grade summary table.

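### The SAP's treatment-emergent AE definition has no worsening clause, so a clinical AE that starts between consent and first dose and rises in grade after dosing can drop out of the TEAE summaries

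*SAP*

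**What the plan says.** - **Definition.** SAP 3.5.1: "Treatment-emergent AE are defined as AEs with onset date during the on-treatment period". SAP 3.5 fixes the start: "The on-treatment period is defined as the period that starts with the first dose of study treatment". The 28-day and the extended 90-day versions of the period differ only in where they end.
- **Second wording.** SAP 6.1.2: "TEAEs is defined as any AE that occurs during the on-treatment period, defined in Section 3.5". It speaks of occurrence rather than onset, and it also says nothing about grade change.
- **Role.** SAP 6.1.2 states "The primary focus will be on TEAEs", for an endpoint that is primary in both parts. SAP 6.4.1 carries the method into Part 2, and SAP 6.9.1 tabulates TEAEs by system organ class and preferred term, grade, seriousness and relationship.
- **How inclusion is decided when a date is missing.** SAP 6.1.2: "The imputed dates will be used to determine whether the AE is to be included in the TEAE summary".
- **Collection.** Under Protocol 8.3.1 the active collection period "begins from the time the participant provides informed consent". Protocol 4.1 allows up to 28 days of screening.
- **Updates.** Protocol 10.3.3, on follow-up of AEs and SAEs: "New or updated information will be recorded in the originally completed CRF". Neither document asks for a new record or a new start date when a recorded AE worsens.

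**The concern.** AE records with a pre-dose start date will exist, because collection runs through a screening period that may include a fresh tumor biopsy. If such an event is mild before dosing and severe afterwards, the post-dose severity is the information a first-in-human safety table is meant to show. A rule based only on start date classes the whole event as not treatment-emergent.

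The effect runs in one direction. It can remove events or lower the worst grade counted, but it cannot add any. It could also make outputs disagree. DLT status rests on Protocol 4.3.3 (SAP 3.5.1 and 6.1.1), not on the TEAE flag, so a worsened screening event could be reported as a DLT and yet be missing from the TEAE table for the same dose level.

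**Working it through.** The plan gives no figure on this point, so the check applies the written rules to one constructed case and then sizes one participant against the planned cohorts.

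**Case (assumed for illustration).** AE onset Day -10 at Grade 1, Grade 3 on Day 5, resolved Day 20. First dose Day 1, last dose Day 15. The on-treatment period with the 28-day tail runs from Day 1 to Day 15 + 28 = Day 43.

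| Rule | Test | Counted? |
|---|---|---|
| SAP 3.5.1, original record kept | is -10 between 1 and 43? | No |
| SAP 3.5.1, new record opened at worsening (not instructed) | is 5 between 1 and 43? | Yes |
| SAP 6.1.2, occurrence read as any overlap | does -10 to 20 overlap 1 to 43? | Yes |
| Onset, or grade increase over pre-dose grade, in the period | is -10 or 5 between 1 and 43? | Yes, at Grade 3 |

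The 90-day tail moves the end to Day 105 (15 + 90) and leaves the first row unchanged. The overlap reading in the third row conflicts with 3.5.1. It would also count screening AEs that never worsened, so it is not a usable substitute.

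**Size of one affected participant.** The shift in incidence is 100/n percentage points. Cohort sizes are from Protocol 9.2.1 (2-4 in Part 1) and 9.2.2 (20-30 in Part 2); intervals are Clopper-Pearson, the method named in SAP 5.2.1.

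| n | 100/n | 0/n, 95% CI | 1/n, 95% CI |
|---|---|---|---|
| 2 | 50.0 | 0-84.2% | 1.3-98.7% |
| 4 | 25.0 | 0-60.2% | 0.6-80.6% |
| 20 | 5.0 | 0-16.8% | 0.1-24.9% |
| 30 | 3.3 | 0-11.6% | 0.1-17.2% |

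**Which events are exposed.** All of the following must hold: the AE starts after consent and before first dose; it is still present at first dose; it rises in grade on treatment; and it stays on one record. The documents give no rate for any of these.

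**The case against.** **The recording link is inferred.** The Protocol 10.3.3 sentence concerns follow-up information in general. It mentions neither a grade increase nor the start date. The CRF guidelines (Protocol 10.1.7) and the sponsor rulebooks (SAP 5.3) are not in the documents. If either opens a new record at a grade increase, the onset rule already captures the event. This stands, and the conclusion is conditional on it. SAP 5.3, however, cites the rulebooks only for imputation.

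**Worsening is recognised elsewhere.** Protocol 10.3.1 treats exacerbation of a preexisting condition as an AE. Pain or fatigue present before consent and held as medical history becomes a new AE, with an on-treatment start, when it worsens. Laboratory worsening such as a falling hemoglobin appears in the baseline-to-worst shift tables of SAP 6.1.3. SAEs, deaths and DLTs are listed separately (SAP 6.9.1). All of this stands and confines the gap to clinical AEs that begin between consent and first dose. It does not close the gap, because neither document says that an AE already on the CRF gets a second record.

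**Collection at screening.** The AE row of the Schedule of Activities shows no mark at screening in the available text. Protocol 8.3.1 is explicit that collection starts at consent, so the premise holds.

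**Stronger readings that the documents do not support.** A reader might infer that such events are missing from every primary safety table. SAP 6.9.1 also summarises participants with any AE, SAE or treatment-related event by worst grade, without calling these treatment-emergent, so that is not established. A reader might also infer that Grade 3 or higher rates are biased downward by some stated percentage. That needs a rate of worsened pre-dose events, which is not given. It would also have to be a share of participants rather than of events: a participant leaves the Grade 3 or higher count only if the worsened event is their sole one at that level.

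**Conclusion.** The gap is real but narrow. As SAP 3.5.1 is written, and if a worsened AE stays on its original record, a clinical AE that starts between consent and first dose and rises in grade on treatment is left out of the TEAE summaries. SAP 6.1.2 does not repair this, and its different wording leaves two definitions to reconcile.

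The effect can only lower reported TEAE incidence and severity. How often it would happen cannot be derived from the documents; given the conditions it needs, it is probably small. It could still be visible in a single cohort: 25 to 50 percentage points per participant in Part 1, and 3.3 to 5.0 points in Part 2. Because DLT determination does not use the TEAE flag and Protocol 9.1 plans no formal hypothesis test, the point concerns the accuracy of the safety tables, not the dose-escalation rule. It should be corrected, since the correction is cheap and the omission is one-sided.

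**What to change.** Use one definition in both SAP 3.5.1 and SAP 6.1.2, for example: *an AE with onset during the on-treatment period, or with onset before first dose and an increase in grade over the pre-dose grade during that period, counted at its worst on-treatment grade.* Apply it to the 28-day and 90-day periods alike.

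To make it workable, choose one of two recording rules:

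1. Keep one record, and capture on it the grade at first dose and the date of any later grade change. If a record holds only the worst grade, the worsening clause cannot be applied.
2. Enter a grade increase after first dose as a new record with its own start date, and reconcile this with the update instruction in Protocol 10.3.3. The new record then qualifies by onset, and the original one does not, so nothing is counted twice.

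These are alternatives; both are not needed. If a sponsor convention already does the second, a sentence in the SAP saying so, together with the aligned definition, is enough. The cost is one SAP clause, slightly more AE data entry and slightly higher reported TEAE rates. Design and sample size do not change.
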